Endpoint	
For the primary and secondary objectives, standardized and validated instruments will be used to measure the following: opioid and other illicit drug use using the timeline follow back method and urine or saliva drug screen (UDS); opioid withdrawal and craving using objective and subjective opioid withdrawal scales (e.g. COWS and SOWS) and visual analogue scales (VAS); level of awareness/sedation using the Richmond Agitation Sedation Scale (RASS), patient reported outcomes of quality of life and functional status using the PROMIS Global 10 and Treatment Effectiveness Assessment (TEA); healthcare utilization using the non-study treatment service use form, participant satisfaction and perceived utility of ED-initiated intervention. Engagement in treatment will be assessed by self-report and/or confirmed by treatment provider. An adverse event log will be maintained.

Study Duration	Duration: 7-10 months
Participant Duration	1 month

Population	Eligible participants will be recruited from the Bellevue Hospital ED and NYULH EDs, which have a large proportion of patients with opioid use disorder (OUD), among other substance use disorders (SUD). Individuals can be selected to participate if they are 18 years and older, speak English, meet DSM-5 criteria for moderate to severe OUD, have used opioids within 7 days, have not used methadone at a dose greater than 30mg within 72 hours or 10mg within 24hours, have objective signs of opioid withdrawal with a COWS score $\geq 8$ or are expected to have a score of this level during their ED visit, are willing and able to participate, and have adequate locator information including access to a phone. Patients will be excluded if they are currently engaged in medication treatment for OUD (methadone, BUP, or naltrexone), are prescribed opioids for treatment of pain, cognitively impaired, in police custody, have an allergy to BUP, receive a dose of BUP greater than 8mg before study enrollment, or have acute medical or psychiatric conditions or co- occurring substance use disorders that are deemed to preclude safe participation, such as recent methadone use. Subjects will also be excluded if they do not have reliable access to a phone or if a 3-hour observation period in the ED is not feasible (may be limited by provider or patient availability).

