### 2.1.3 Study Rationale

#### *Study Rationale and Dose Rationale*

Under most current BUP induction guidelines, only a partial induction is feasible during a brief ED visit, where 8mg is given in divided doses of 2-4mg. Thereafter, a maintenance dose is reached ranging from 16 to 32mg, but this is not currently achieved during ED visits. The threshold for suppressing withdrawal and the rewarding effects of an opioid challenge occurs when greater than 70% of  $\mu$ -opioid receptors are occupied, which typically occurs at plasma BUP concentrations of  $\geq 2$ ng/mL. Patients discharged after administration of  $\leq 8$ mg SL BUP may have both incompletely treated acute withdrawal symptoms and return of opioid craving within only 4 hours. Thus, a patient would need to successfully navigate a complex medical system to obtain BUP for continued unobserved induction – and would have return of withdrawal and craving if not done within a certain period of hours. In real-world settings, without the heavily supported conditions present in the published trials, high rates of failure to engage in treatment after ED discharge have been observed.

Administration of a larger 32mg SL BUP dose during the ED visit may improve engagement in OUD treatment by producing both a greater reduction in opioid withdrawal intensity during the ED stay and prolonged suppression of opioid craving after discharge. A rapid ED induction eliminates the need for an unobserved induction after discharge, which relies on immediate access to prescribed buprenorphine and patient compliance with complex titration instructions. Current data suggest both fewer acute withdrawal symptoms and increased duration of effect with BUP doses  $\geq 8$ mg SL. Among heroin-dependent patients presenting with acute withdrawal treated with 8mg SL BUP, Oreskovich *et al.* observed a mean reduction in Clinical Opioid Withdrawal Scale (COWS) score from 15 to 8. In a similar population, using 24mg SL BUP, Ang-Lee *et al.* observed a much larger mean reduction in COWS from 17 to 2 with withdrawal suppression lasting  $>72$  hours. Whitley *et al.* found that compared to higher doses, a low initial dose of BUP (2mg SL) was associated with increased rates of protracted withdrawal and treatment failure.

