### 5.1.2 Secondary Study Endpoints

#### 1. To evaluate opioid withdrawal, opioid craving, sedation during of index ED visit:

We will estimate the change in signs and symptoms of opioid withdrawal, opioid craving, level of awareness (activation/sedation) and other medication effects at repeated points of assessment during the index ED visit (spanning from enrollment in the study to a minimum of 90 minutes after the second dosage of BUP) using validated subjective and objective instruments and physiologic measures. For each domain (withdrawal, craving, sedation), we will determine the proportion of participants who experience changes in the specified measures and assess the magnitude of change and the time to change comparing repeated measures assessed during the index visit before treatment, after the first dose of BUP, and after the second dose of BUP.

The primary measures for opioid withdrawal and craving will be the Clinical Opiate Withdrawal Scale (COWS) and Opiate Craving Scale (OCS), respectively. Complete or near complete relief of withdrawal and craving will be assessed primarily by the point at which patient reports this endpoint ("Tell me when your withdrawal/craving has gone away completely"); we will secondarily note when patient has COWS score, Likert, or VAS score indicating absence of withdrawal or craving. Near complete relief will be assessed secondarily as "gone away almost completely" and using a COWS score of <3. Oversedation will be defined clinically as the need for non-invasive or invasive ventilation to maintain adequate oxygenation and ventilation; the Richmond Agitation Sedation Scale (RASS) will be used secondarily to assess level of awareness (the spectrum of sedation to agitation). Relief of (or recovery from) sedation is when invasive or non-invasive ventilator support is no longer required, with a RASS > -2, and when patient is alert enough for discharge as determined by the treating clinician. Specific measures and times of assessment are further described in and Section 4.2.1 (Study Measures) and Section 7 (Study Procedures).

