### **6.9.4 Dosing and Administration**

All participants will receive a total dose of BUP 32mg sublingually in divided doses during the index ED visit. After the participant has received a total of 8mg (as a single dose or in divided doses), BUP SL 24mg will be administered (i.e., 8mg + 24mg, or 4mg + 4mg +24mg). A dose of up to BUP 8mg SL may be administered by the clinical provider prior to enrollment of the patient-participant (i.e., given clinically, not as a research procedure).

After pre-medication assessments are complete and the participant is confirmed to have a COWS of  $\geq 8$ , the participant will be given BUP SL to reach a dose of 8mg. Starting 30 minutes after BUP administration, the participant will be reassessed for withdrawal severity and any adverse events. As long as there are no unexpected significant adverse events, an additional BUP 24mg SL will be administered. Then, participants will be monitored and reassessed every 30 minutes for a period of at least 90 minutes after receiving the last dose of BUP.

Participants will return on days 1, 2, and 3 for research visits. At those visits, participants will be assessed for opioid withdrawal using the COWS scale. On the first day that the participant has objective signs of opioid withdrawal (via COWS), the [name], who is a licensed physician with an X-waiver for BUP prescription, or another study clinician (with the appropriate license and X-waiver) will electronically send a prescription the participant's preferred outpatient pharmacy for a daily dose of BUP 16mg (BUP or BUP/NX 8/2mg: two SL) to start immediately. Participants will be prescribed a quantity sufficient to ensure medication coverage until the date of their appointment for ongoing treatment with a (non-study) OUD treatment provider. Participants who do not exhibit opioid withdrawal at any of the visits on days 1-3, will be given a prescription upon completion of the day 3 visit with instructions to self-administer upon emergence of symptoms of opioid withdrawal or craving.

All participants will receive a referral to be seen by a provider experienced in treating OUD. Thereafter, continued treatment and specific daily dosage of BUP-NX will be a joint decision between the study participant and the healthcare provider.

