## **7 Study Procedures and Schedule**

### **7.1 Study Specific Procedures**

#### *Baseline Measures*

At baseline, socio-demographic information will be collected including age, sex, race/ethnicity, and housing status.. A broad range of tools selected from the Study Measures will be assessed at baseline and repeated at subsequent visits, include measures of substance use, opioid withdrawal and craving, risk behaviors, and quality of life. A urine pregnancy test will be used to confirm study eligibility among females of childbearing potential unless one has been performed already clinically. A urine and/or saliva toxicology test (standard drug panel plus BUP and fentanyl) will be collected for research-only purposes. No study-related activities will be performed prior to obtaining written informed consent.

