### **7.2 Standard of Care Study Procedures**

As part of standard clinical care, patients in opioid withdrawal will have a basic history and physical examination completed, including many of the assessments we will complete as study measures (e.g., drug use screening, DSM5, COWS). The provider may choose to obtain basic bloodwork and/or urine testing as indicated by clinical signs and symptoms or in anticipation of treatment. This includes, but is not limited to, a pregnancy test. Toxicology tests are not routinely obtained clinically in the ED primarily because the available tests are not capable of detecting fentanyl (or most other synthetic opioids) and because there are reliable, objective clinical signs and symptoms of opioid intoxication and withdrawal. It would be considered unethical to require toxicology testing to demonstrate the presence of opioid use in order for a patient to receive life-saving treatment (i.e., BUP) when the test itself cannot detect one of the most prevalent opioids being used. As such, toxicology testing in the ED is of little utility.

Whether they consent to study participation or not, all patients who present in clinical opioid withdrawal can receive symptomatic treatment for withdrawal. If an X-waivered provider is available in the ED, the patient will be able to receive BUP according to that provider's usual clinical practice. Patients with OUD can also receive referral for outpatient treatment and follow-up, as clinic availability allows

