## **7.4 Study Schedule**

### **7.4.1 Screening**

### **7.4.2 Enrollment/Baseline**

#### **Index ED Visit (Day 0, 4 – 8 hours)**

- Perform baseline assessments:
  - Obtain demographic information, medical/psychiatric history, medication history, substance use history.
  - Obtain informed consent of potential participant verified by signature on written informed consent for screening form.
  - Perform medical examinations needed to determine eligibility based on inclusion/exclusion criteria.
  - Review history and verify inclusion/exclusion criteria.
  - Collect urine or saliva samples for toxicology testing, collect urine for a pregnancy test (in females of childbearing potential, if not performed clinically).
  - Assess and quantitate opioid and other substance use, withdrawal, craving, motivation for treatment, health status questionnaire, health services utilization).
- Participants receive total 32mg BUP in divided doses. After the participant has received a total of 8mg, participants will be observed for 30 minutes to ensure that there are no adverse reactions to BUP-NX. If the participant has a qualifying adverse event after the first dose (e.g., allergic reaction or other clinically significant AEs as described in Section 5.1.1), the second dose will not be given and the participant will be withdrawn from the study without receiving subsequent doses. Otherwise, the second dose of 24 mg will be administered.
- Participants will be assessed using opioid withdrawal scales (COWS, SOWS, VAS) prior to BUP administration and every 30 minutes afterward for at least 90 minutes after last dose.
- Participants will be discharged with 4 scheduled appointments, 3 research visits (days 1, 2, 3), an appointment for follow up with a BUP provider for ongoing OUD treatment, and a research follow-up phone call on Day 30, which marks the end of the study for the participant.
- In light of the health safety risks associated with the COVID-19 pandemic, interviews may be conducted remotely, rather than in-person, using an approved, secure audio or audio-video connection (e.g., telephone, Cisco Webex) from a setting offering adequate privacy. Participants will be advised that they may disconnect their video feed.

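### For participants given buprenorphine before enrolment, secondary endpoint 1 has no defined pre-treatment baseline or time origin

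*Combined protocol and SAP*

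**What the plan says.** Section 6.9.4 states that "A dose of up to BUP 8mg SL may be administered by the clinical provider prior to enrollment of the patient-participant", as clinical care and not as research. The Protocol Summary is consistent with this: it excludes only patients who "receive a dose of BUP greater than 8mg before study enrollment". The participant is then brought up to 8 mg where needed, and the 24 mg dose follows.

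Secondary endpoint 1 (Section 5.1.2, item 1) covers withdrawal, craving and sedation at the index visit. Its window is given as "spanning from enrollment in the study to a minimum of 90 minutes after the second dosage of BUP". The proportion changing, the size of the change and the time to change all come from "comparing repeated measures assessed during the index visit before treatment, after the first dose of BUP, and after the second dose of BUP". Section 7.4.2 has the withdrawal scales taken "prior to BUP administration and every 30 minutes afterward for at least 90 minutes after last dose", and the schedule in Section 1.1.1 also places an assessment ahead of dose 1.

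Section 7.1 adds: "No study-related activities will be performed prior to obtaining written informed consent". Section 6.4 says the same.

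On usual care, Section 7.2 says: "As part of standard clinical care, patients in opioid withdrawal will have a basic history and physical examination completed, including many of the assessments" that the study also uses, and it names COWS among them. For the effect of 8 mg, Section 2.1.3 cites a study that "observed a mean reduction in Clinical Opioid Withdrawal Scale (COWS) score from 15 to 8".

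Section 10.1 plans descriptive summaries. It does not define baseline or mention buprenorphine given before enrolment.

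**The concern.** A participant who arrives in the study with buprenorphine already on board cannot supply a research score from before treatment. Their first research COWS, SOWS, craving and RASS values come after part or all of the first 8 mg. If that value is entered as baseline, the relief already obtained is lost from the measured change. Any time to change counted from enrolment also starts after the drug did.

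Participants who were not pre-dosed have a true baseline. Pooling the two groups puts different quantities under one label. A descriptive mean change, proportion improved or time to relief is only interpretable if its zero point is the same for everyone.

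The same baseline feeds two other analyses: the cross-tabulation by baseline withdrawal score (Protocol Summary) and the exploratory link between index-visit change and duration of effect (Section 5.1.3). These results are meant to inform the design of the next trial.

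**Working it through.** There is no power or precision figure to reproduce. Section 10.1 bases the sample of 35 on feasibility. The check has two parts.

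**1. What each participant's first research score represents**

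| Buprenorphine before enrolment | First research score | Is a score from before treatment available to the endpoint? |
|---|---|---|
| None | Before any buprenorphine | Yes |
| Part of the 8 mg (e.g. 4 mg) | Between the two parts of the first 8 mg | Not from research staff |
| All 8 mg | After the whole first step | Not from research staff; the before-treatment and after-dose-1 values may coincide |

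The plan does not say whether the clinical dose counts as dose 1, or which event starts the clock.

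**2. Size of the effect on the pooled mean change in COWS**

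Formula: measured mean change = true mean change − f × r.

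- f is the share of participants pre-dosed. The documents do not give it, so 10%, 25% and 50% are shown.
- r is the mean fall in COWS between the clinical dose and the research baseline. It is assumed to be 2 to 7. The upper value is the fall cited in Section 2.1.3 for 8 mg: 15 − 8 = 7.

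| f | r = 2 | r = 3.5 | r = 7 |
|---|---|---|---|
| 10% | 0.2 | 0.35 | 0.7 |
| 25% | 0.5 | 0.875 | 1.75 |
| 50% | 1.0 | 1.75 | 3.5 |

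For scale only, Section 2.1.3 cites a 24 mg study with a fall from 17 to 2, or 15 points. Against 15, the r = 7 column is 0.7/15 = 5%, 1.75/15 = 12% and 3.5/15 = 23%. The r = 2 column is 1%, 3% and 7%.

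The contrast from before treatment to after dose 1 is more exposed. If its true value is 7 and r = 7, the pooled value is 7 − 7f: 6.3, 5.25 and 3.5 at the three shares.

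**If the COWS check of 8 or more is applied after the clinical dose.** A simulation assumed pre-dose COWS with mean 15 and SD 4 or 5, an 8 mg effect with mean 7 and SD 3 or 4, and a final score of 2. About 52% to 54% of pre-dosed patients then pass the check. Their mean measured change is 10.0 to 11.1 against a true 15.3 to 16.1, about 5 points short. The means and SDs are illustrative.

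**The case against.** The strongest reply is that the gap can be filled from material the plan already has. Section 2.1.4 calls for a formal assessment of withdrawal severity before any buprenorphine. Section 7.2 puts COWS in usual care, Section 2.1.5 describes charting of such assessments, and Section 4.2 lists record abstraction as a data source. This stands in part. A reader might infer that no pre-treatment COWS will exist for these participants, and the documents do not support that. What is missing is any rule making the charted value the endpoint baseline. For craving and SOWS the reply is weaker, because usual care is not said to include them.

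Second, Section 6.7.1 says that only the 24 mg step is under evaluation. For that step a score taken after 8 mg is the right reference, and this part of the reply stands. But Section 5.1.2 asks for a comparison with values before treatment, and the matching objective in Section 3.2 concerns change after 32 mg.

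Third, the analyses are descriptive and the primary endpoint uses no baseline score. Both are true. They limit the importance of the point but do not repair the summaries.

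Two stronger readings are tempting. One is that a fall from 15 to 2 would be recorded as 8 to 2, losing 7/13 = 54% of the effect. Section 2.1.3 does not support this: the 15-to-8 and 17-to-2 figures come from different studies, and neither shows a later dose moving COWS from 8 to 2. A mean baseline of exactly 8 also cannot hold if every admitted score is at least 8 and scores vary. The other reading is that good responders to the clinical dose are certain to be screened out. Section 6.9.4 does not say whether the COWS check is read before or after that dose, so this selection is only possible.

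**Conclusion.** The point holds as an undefined baseline and time origin in secondary endpoint 1, limited to participants given buprenorphine before enrolment. Followed as written, the plan gives them a post-dose research baseline and pools them with participants who have a true one.

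Understatement of the change in withdrawal and craving is the likelier direction, on the premise that the clinical dose relieves symptoms. It could reverse in a participant whose withdrawal worsened after that dose.

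The documents do not fix the size. It is f × r COWS points and rests on two assumptions, the pre-dosed share and the earlier fall. The 7-point end of the range supposes that all 8 mg was given and had its full effect before the research baseline. Section 6.9.4 allows less than 8 mg, and Section 2.1.3 does not say when the score of 8 was taken. The plan should be changed on this point, but the primary result does not depend on it.

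**What to change.** In Section 5.1.2, item 1, and Section 10.1:

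- Record the amount and time of any buprenorphine given before enrolment.
- Define baseline COWS as the last score before any buprenorphine in the ED visit, abstracted from the chart where research staff could not take it.
- Where no such score exists, as is likely for craving and SOWS, treat it as missing. Leave that participant out of the contrasts that need a before-treatment value, including the one to after dose 1.
- Start time to change at the first buprenorphine dose of the visit.
- Show pre-dosed and not-pre-dosed participants in separate rows.
- Report the change from after dose 1 to after dose 2 as its own contrast for the 24 mg step, with the post-8 mg score as reference.

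Sections 2.1.4, 5.1.2, 6.7.1, 6.9.4 and 7.4.2 should be reconciled on what counts as before treatment and as dose 1, and on when the COWS check is read relative to a clinical dose. None of this requires a change to dosing or eligibility.

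The cost is chart abstraction and a few lines of analysis text. There are two downsides. Baseline COWS would mix clinician-charted with research-rated scores, so the source should be flagged. The craving and SOWS rows would lose participants in proportion to the pre-dosed share: of 35, about 3 or 4 at 10% (3.5), 9 at 25% (8.75) and 17 or 18 at 50% (17.5).

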#### **2.1.2 Clinical Data to Date**

A small handful of studies to date have demonstrated the safety and effectiveness of high dose BUP induction, ranging from case reports to randomized controlled trials. Ang-Lee et al. observed a significant mean reduction in Clinical Opioid Withdrawal Scale (COWS) score in heroin-dependent patients using 24 mg SL BUP. Furthermore, participants in this small open-label study did not experience any significant adverse events, aside from one participant who had precipitated withdrawal which resolved within 4 hours, and withdrawal suppression lasted >72 hours. A similar study by Kutz et al. treated 10 heroin-users in acute withdrawal with 32 mg BUP (8mg every 5 minutes for 20 minutes), and reported that nine of the participants completed detoxification with negligible withdrawal symptoms, with suppression also lasting > 3- 4 days. Again, no adverse events were reported.

Within the past two years, four randomized controlled trials out of Iran have provided evidence that high dose BUP for opioid withdrawal is both safe and reduces craving/withdrawal over an extended time frame following initial administration. One of these studies randomized 90 opioid-dependent men in withdrawal to three groups to receive single doses of 32 mg, 64 mg, and 96 mg respectively. They observed a significant reduction in craving symptoms using a Visual Analogue Scale (VAS) in all three cohorts that was more pronounced at 64 mg than 32 mg, but no greater effect was observed at 96 mg. The resolution of craving was maintained at 5 days post initial treatment. Only four participants developed side effects, which included hypotension, nausea and vomiting (expected side effects of BUP even at low doses), all of which resolved with hydration and anti-emetics. This research group also published a recent case report of heroin detoxification using 120 mg SL BUP in a single patient experiencing severe withdrawal. Withdrawal suppression persisted for 4 days after initial administration, and the patient was discharged without need for additional buprenorphine. There were no side effects or adverse events reported in this case.

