## 4 Study Design and Endpoints

### 4.1 Description of Study Design

This is an open-label, single arm, single site feasibility and acceptability study in which 35 ED patient-participants who have untreated moderate to severe OUD and are experiencing opioid withdrawal (COWS score  $\geq 8$ ). will receive treatment in the ED with a loading dose of BUP 32mg SL (administered in divided doses) at their index visit. We will assess the feasibility, acceptability, safety, and utility of this intervention and provide preliminary data on the effect on opioid withdrawal, craving, and sedation as well as additional patient-level outcomes (engagement in treatment, drug use, quality of life, healthcare utilization).

The first assessment will occur in-person in the ED at the index visit (day 0), and 4 additional appointments will be scheduled: 3 research visits and one follow-up care appointment with an OUD provider. Research assessments will be conducted in-person at clinical research space on Bellevue/NYULH campus on days 1-3, and by phone on day 30. Patients will be provided with appointment reminder cards with the time and location of their next appointment, and the contact information for the research study team. At the conclusion of their day 3 visit, participants will be given a prescription for BUP SL 16mg per day with a quantity sufficient to last until their scheduled clinical follow up appointment for ongoing treatment. The prescription will be provided earlier, at the day 1 or day 2 research visit, if the participant reports opioid withdrawal and/or craving and has objective signs of withdrawal at that time.

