### **7.4.3 Intermediate Research Visits**

#### **7.4.3.1 Research Visits (In person, Days 1-3, 30-60 minutes)**

- Participants will complete assessments of withdrawal, craving, and substance use in-person daily for 3 days. The visits will occur either at the ED or at other clinical research space on Bellevue/NYU campus. In light of the health safety risks associated with the COVID-19 pandemic, interviews may be conducted remotely, rather than in-person, using an approved, secure audio or audio-video connection (e.g., telephone, Cisco Webex) from a setting offering adequate privacy. Participants will be advised that they may disconnect their video feed.
- Participants will assess themselves for symptoms of opioid withdrawal using subjective scales
- At the first visit (Day 1-3) in which the participant has objective signs of withdrawal, the participant will be provided with a prescription for BUP. If the participant does not have objective signs of withdrawal by the Day 3 visit, the prescription will be written at the conclusion of that visit. The prescription will be electronically sent to the participant's pharmacy for BUP or BUP/Nx 8/2mg: 2 films/tabs taken SL daily for each day, starting immediately, with a quantity sufficient to last until the scheduled appointment for

Study Number: s19-01700

Version: 7.0

Version Date: 08/01/2022

ongoing treatment)

- Participants will be assessed for adverse events, which will be recorded and reported.

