## 10 Statistical Considerations

### 10.1 Statistical and Analytical Plans (SAP)

The overall findings of the study will be used to assess the feasibility, acceptability, and utility of initiating a BUP loading dose in ED patients and linking patients to ongoing OUD treatment. Statistical analyses will consist of descriptive analyses for the primary outcome (proportion of participants successfully induced via loading dose), and secondary outcome measures (opioid withdrawal and craving scores, time to next BUP dose, opioid and other illicit drug use, proportion making a successful transition to an outpatient clinic). Measures of central tendency (the mean), and the variability (standard deviation) of the study participant characteristics and for other participant-reported or objectively evaluated measures will also be calculated. Summary tabulations and measures of central tendency, variance, and other distributional properties of the obtained results will be presented. Where applicable, we will also conduct cross-tabulations and comparative analyses of variance based on selected key characteristics of the study participants (e.g., sex, age categories, baseline opioid requirement). This is a pilot study aimed at producing preliminary data which will inform future large-scale studies. Our analyses will be purely descriptive and we will not attempt to show an effect size, thus there is no power calculation for this sample size, it is based on feasibility.

Our a priori hypotheses of the potential effect of patient characteristics on outcomes will be tested in subsequent large scale studies. The outcomes obtained in the proposed pilot study will also be compared with benchmark data based on the results of our previous studies with similar patient populations and other available recent or contemporaneous research and clinical data. Adverse events recorded in the study will be reported using both quantitative tabulations and qualitative descriptions.

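### For participants with no objective withdrawal through Day 3, sections 6.9.4 and 7.4.3.1 contradict each other on when to start the prescribed BUP, and in that group time to next BUP dose depends on which is followed

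*Combined protocol and SAP*

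**What the plan says.** Section 6.9.4 separates two groups after the index visit. A participant with objective withdrawal (by COWS) on Day 1, 2 or 3 gets a prescription for daily BUP 16 mg, "BUP or BUP/NX 8/2mg: two SL) to start immediately". A participant with no withdrawal at any of those visits gets a prescription after the Day 3 visit, "with instructions to self-administer upon emergence of symptoms of opioid withdrawal or craving".

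Section 7.4.3.1 names the same two groups. For those without objective signs by Day 3, "the prescription will be written at the conclusion of that visit". Its next sentence describes the prescription once, for both groups: "2 films/tabs taken SL daily for each day, starting immediately, with a quantity sufficient to last until the scheduled appointment for" ongoing treatment. No exception is made for the no-withdrawal group.

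Section 10.1 lists "time to next BUP dose" among the secondary outcomes. It gives no time origin, event definition, censoring rule or data source. (The Study Measures List that section 4.2.1 refers to is not part of the document reviewed, so a data item may exist there.)

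Section 4.1 allows a prescription at the Day 1 or Day 2 visit "if the participant reports opioid withdrawal and/or craving and has objective signs of withdrawal at that time". Sections 6.9, 6.9.4, 6.9.6 and 7.4.3.1 ask for objective signs alone.

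**The concern.** A prescriber facing a symptom-free participant at the end of Day 3 cannot obey both sections. That is a fault in an instruction to patients whatever its effect on the analysis.

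It also reaches the analysis. In time to next BUP dose, the event is taking BUP again. If the no-withdrawal group is told to start at once, the event is produced by the instruction. The participants in whom the 32 mg dose worked longest are then all recorded at about Day 3. If they are told to wait for symptoms, the time still carries information about how long the dose lasted. If staff vary, the recorded times in this group mix two quantities and cannot be summarised as one. The protocol's case for the loading dose is that it bridges the gap to follow-up care, so times beyond Day 3 are informative about that case.

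**Working it through.** The plan has no figure to reproduce. Section 10.1 states that there is no power calculation and that the analyses are descriptive. The check is a comparison of texts followed by an illustration of size.

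**Texts side by side**

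- Objective withdrawal on Day 1, 2 or 3: both 6.9.4 and 7.4.3.1 say to start at once. No conflict.
- No objective withdrawal through Day 3: 6.9.4 says on symptoms, 7.4.3.1 says at once. Conflict.
- Sections 4.1, 6.9, 6.9.1, 6.9.6 and 6.9.10 also describe the prescription. None says when the no-withdrawal group starts it.

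**Where the cap falls.** The Day 3 visit is about 3 × 24 = 72 h after the index visit. Section 2.1.2 cites withdrawal suppression beyond 72 h after 24 mg, beyond 3-4 days after 32 mg, and, in a trial of 32, 64 and 96 mg, "The resolution of craving was maintained at 5 days post initial treatment". Section 2.1.3 is more cautious and expects 32 mg to work for 24 hours or more. A cap at 72 h may therefore bind for many participants or for few.

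**Illustration.** The assumptions here are not from the documents: duration of effect D lognormal with median m and log-SD 0.5; visits at 24, 48 and 72 h; next dose taken at the first visit showing withdrawal; full adherence. If D > 72 h, the next dose is taken at D (instruction A, on symptoms) or at 72 h (instruction B, at once).

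- Share reaching the end of Day 3 without signs = 1 − Φ(ln(72/m)/0.5). For m = 36: ln 2/0.5 = 1.386, share 8%. For m = 72: 50%.
- Number affected = 35 × share.
- Difference in means, A − B = E[max(D − 72, 0)] = m·exp(0.125)·Φ((ln(m/72) + 0.25)/0.5) − 72·Φ(ln(m/72)/0.5). For m = 72: 81.6 × 0.691 − 72 × 0.5 = 20.4 h.

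Simulated results (400,000 draws per row), which agree with these formulas:

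| True median (h) | Share without signs at Day 3 | Of 35 | Mean A (h) | Mean B (h) | Median A (h) | Median B (h) |
|---|---|---|---|---|---|---|
| 36 | 8% | 3 | 51 | 50 | 48 | 48 |
| 48 | 21% | 7 | 64 | 58 | 72 | 72 |
| 72 | 50% | 18 | 87 | 67 | 72 | 72 |
| 96 | 72% | 25 | 112 | 70 | 96 | 72 |
| 120 | 85% | 30 | 138 | 71 | 120 | 72 |

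Under B neither the mean nor the median can pass 72 h. The means differ by 51.4 − 49.7 = 1.7 h in the first row and by 137.7 − 71.2 = 66.5 h in the last. The medians differ only when more than half the sample reaches Day 3 without signs. On the 30 participants the protocol hopes will complete, the affected numbers are about 30 × 0.08 = 2 to 30 × 0.85 = 25.

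**The trigger.** Section 4.1 differs from the other sections only for someone who has objective signs on Day 1 or 2 but reports neither withdrawal nor craving. The other sections give that person a prescription at that visit; 4.1 does not. Secondary endpoint 3 (section 5.1.2) counts participants who need a BUP prescription on Days 1-3 and the time to that event, so this component can change with the trigger applied. Such participants are probably few.

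**The case against.** The strongest reply is that duration of effect is measured elsewhere. Objective 4 and secondary endpoint 3 assess it on Days 1-3 through withdrawal, craving, return to opioid use and need for a prescription. All of these are observed by the end of the Day 3 visit, before the disputed instruction operates. Time to next BUP dose appears once, in a descriptive list, and is not named as the duration measure. This stands, and it limits the consequence. It does not remove the contradiction, and it leaves a named outcome without a settled meaning in one group.

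It can also be said that 6.9.4 is the dosing section and alone addresses this group's start separately, so that 7.4.3.1 is merely loose. That may be what was intended, but the text does not say so.

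A reader might infer that the outcome measures the instruction and not the drug in general. The documents do not support that. Participants with objective withdrawal on Days 1-3 get the same instruction in both sections (their times are only rounded to daily visits), and under 6.9.4 the later times still follow symptoms. A reader might also infer that much of the sample is affected. The prior durations in section 2.1.2 make that plausible, but no figure in the plan establishes it, and a short true duration would leave few affected.

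**Conclusion.** The contradiction is confirmed from operative text and is confined to participants with no objective withdrawal through the Day 3 visit. For them, time to next BUP dose is capped near 72 h under 7.4.3.1 and follows symptoms under 6.9.4; mixed use gives values that are not comparable. The cap assumes that participants fill the prescription and take it as told. The size cannot be derived from the documents: about 3 to 30 of 35, and a shift in the mean of about 2 to 66 h, hold only under the assumed durations.

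The primary endpoint is decided at the index visit and is unaffected. The Day 1-3 duration measures are unaffected by the start instruction. The trigger difference in section 4.1 is a lesser point that touches one component of secondary endpoint 3. The matter is worth correcting because the correction is cheap, but it does not undermine the study.

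**What to change.** Reconcile 6.9.4 and 7.4.3.1 to one start instruction for the no-withdrawal group, and 4.1, 6.9, 6.9.4, 6.9.6 and 7.4.3.1 to one trigger for the earlier prescription. Which instruction and which trigger is for the sponsor's clinicians to decide.

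In section 10.1, define time to next BUP dose as the time from the 24 mg dose to the first subsequent BUP dose taken. Record the start instruction each participant received. Ask for the first-dose date at the Day 30 call, where section 6.9.9 already has adherence reported.

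If the reconciled instruction for the no-withdrawal group is not symptom-triggered, censor that group at the Day 3 visit whenever the outcome is used to estimate duration of effect. Do not extend this to every dose taken on instruction. Doses started after objective withdrawal on Days 1-3 should stay as events, because censoring them would remove participants at the moment the effect was lost.

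The cost is wording in existing sections, one definition and two data items. The downsides are that first-dose dates after Day 3 rest on recall, and that censoring leaves fewer observed times in a sample of 35.
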